1. LIST OF ABBREVIATIONS

ACPR	Adequate clinical and parasitological response
ACT	Artemisinin-based combination therapy
AE	Adverse event
AL	Artemether-lumefantrine
AQ	Amodiaquine
AS	Artesunate
ASMQ	Artesunate-mefloquine
AUC	Area under the (plasma concentration-time) curve
CRF	Case record form
CTSG	Clinical Trials Support Group (MORU)
CYP3A4	Cytochrome P450 3A4
DHA	Dihydroartemisinin
DNA	Deoxyribonucleic Acid
DSMB	Data and Safety Monitoring Board
EDC	Electronic data capture
EDTA	Ethylene-diamine-tetra-acetic acid
ERB	Ethics Review Board
G6PD	Glucose-6-phosphate dehydrogenase
GCP	Good Clinical Practice
Hb	Haemoglobin
Hct	Haematocrit
IM	Intramuscular
IV	Intravenous
MORU	Mahidol-Oxford Research Unit
MQ	Mefloquine
NMCP	National Malaria Control Programme
OxTREC	Oxford Tropical Research Ethics Committee
PBO	Placebo
PCR	Polymerase Chain Reaction
PCT	Parasite Clearance Time
PD	Pharmacodynamic
Pfmdr1	P. falciparum Multi-Drug Resistance Gene 1
PK	Pharmacokinetic
PPQ	Piperaquine
QA	Quality Assurance
QC	Quality Control
RNA	Ribonucleic acid
SAE	Serious Adverse Event
SNP	Single-nucleotide polymorphism
TACT	Triple Artemisinin-based Combination Therapy
TRAC	Tracking Resistance to Artemisinin Collaboration
WBC	White Blood Cells
WHO	World Health Organisation

WI Work Instruction
WWARN Worldwide Antimalarial Resistance Network

2. SYNOPSIS

Study Title	A multi-centre, randomised, controlled non-inferiority trial to compare the efficacy, safety and tolerability of Triple Artemisinin-based Combination Therapies versus first-line ACTs + placebo for the treatment of uncomplicated Plasmodium falciparum malaria in Africa
ACRONYM	DeTACT-Africa
Trial Design	A partially blinded randomised controlled non-inferiority trial comparing the efficacy, tolerability and safety of Triple ACTs artemether-lumefantrine+amodiaquine (AL+AQ) and artesunate-mefloquine+piperavaquine (ASMQ+PPQ) and the ACTs artemether-lumefantrine+placebo (AL+PBO), artesunate-mefloquine+placebo (ASMQ+PBO) (with single-low dose primaquine in some sites) for the treatment of uncomplicated Plasmodium falciparum malaria to assess and compare their efficacy, safety, tolerability.
Trial Participants	Subjects with acute uncomplicated P. falciparum malaria
Sample size	Estimated total sample size up to 3240 subjects recruited at 8 sites in Africa (Burkina Faso, DRC, The Gambia, Guinea, Niger, Nigeria, Rwanda, Tanzania) 
 - In Rwanda only – 216 subjects - All other sites – 432 subjects per site
Inclusion Criteria	
 • Male or female, aged ≥ 6 months to < 12 years (For Gambia, Rwanda sites only: ≥ 6 months) • Ability to take oral medication • Acute uncomplicated P. falciparum mono-infection • Asexual P. falciparum parasitaemia: 1,000/μL to $\leq 10\%$ parasitaemia, determined on a peripheral blood film (At Gambia, Rwanda sites only: For subjects ≥ 12 years – 1000/μL to 200,000/μL) • Fever defined as $\geq 37.5^{\circ}\text{C}$ tympanic temperature or a history of fever within the last 24 hours • Written informed consent by the subject or by the parent/guardian in case of children lower than the age of consent and assent if required (per local regulations) • Willingness and ability of the subjects or parents/guardians to comply with the study protocol for the duration of the study

Exclusion Criteria	
 • Signs of severe malaria (adapted from WHO criteria, see section 8.4) • Patients not fulfilling criteria for severe malaria but with another indication for parenteral antimalarial treatment at the discretion of the treating physician • Haematocrit <15% at screening (For Gambia, Rwanda sites only: For subjects ≥12 years – Haematocrit <20% at screening) • Subjects who have received artemisinin or a derivative within the previous 7 days OR lumefantrine or amodiaquine within the previous 14 days OR mefloquine or piperaquine within the previous 30 days • In applicable countries: use of seasonal malaria chemoprophylaxis (SMC) within the last 14 days. • Acute illness other than malaria requiring systemic treatment; • Severe acute malnutrition (in Niger only – only those patients with Severe Acute Malnutrition and complications requiring inpatient nutritional treatment will be excluded) • Known HIV infection • Known tuberculosis infection • For females: post-menarche (For Gambia, Rwanda sites only: females who are pregnant, trying to get pregnant or are lactating) • History of allergy or known contraindication to any of the study drugs, including neuropsychiatric disorders and epilepsy • Previous splenectomy • Enrolment in DeTACT in the previous 3 months • Participation in another interventional study in the previous 3 months
Planned Trial Period	Projected recruitment of 21 months: September 2020 to June 2022; study projected to finish in March 2023.
Primary Objective	To compare the efficacy of the ACTs and TACTs as defined by the 42-day PCR corrected adequate clinical and parasitological response (ACPR) within each individual site
Secondary Objectives	
 • To compare the safety and tolerability of ACTs and TACTs within and across sites and regions, including comparisons of ‘non-matching’ ACTs vs TACTs (AL+PBO versus ASMQ+PPQ, ASMQ+PBO versus AL+AQ).

	
 To compare additional measures of treatment efficacy between treatment arms, including the 63-day ACPR, the post-treatment prophylactic effect of ACTs and TACTs defined as the 42-day & 63-day PCR uncorrected ACPR, gametocyte carriage, parasite clearance rates and fever clearance. To assess pharmacokinetic and pharmacodynamic interactions between antimalarials in TACTs
Exploratory Objectives	
 To assess molecular genetic and transcriptomic correlates for artemisinin and partner drug resistance of the infecting P. falciparum strains and to assess their ex vivo and in vitro drug susceptibility. To compare the selective effect of ACTs versus TACTs on parasites carrying mutations associated with resistance to antimalarial drugs To obtain additional safety data (in particular incidence, rate and magnitude of haemolysis) on the deployment of single low dose primaquine, stratified according to G6PD status/genotype To obtain additional data on the effect of the host genotypes known to affect pharmacokinetics and pharmacodynamics of antimalarials To obtain data on the place of residence, work, recent travel history and mobile phone usage in order to improve the understanding of local malaria transmission by identifying behaviours and risk factors associated with malaria infection and possible routes of spread of malaria and artemisinin resistance To assess new methods for determination of gametocytaemia, parasite phenotypes and genotypes To assess the correlation between anti-Plasmodium falciparum antibodies and drug efficacy measures To assess the prevalence of parasites carrying complete or partial deletions in pfhrp2 gene
Primary endpoint	42-day efficacy defined as PCR-corrected adequate clinical and parasitological response (ACPR).
Secondary endpoints	
 For safety and tolerability: Incidence of adverse events and serious adverse events within the first 42 days including markers of hepatic, renal or bone marrow toxicity; cardiotoxicity, in particular QT or QTc-interval above 500 ms at

	
timepoint H4 and H52/H64 and between these time points; change in haemoglobin concentration at day 3, 7, 28, stratified for G6PD status/genotype; proportion of subjects requiring retreatment due to vomiting within 1 hour after administration of the study drugs; proportion of subjects that reports completing a full course of observed TACT or ACT without withdrawal of consent or exclusion from study because of drug related serious adverse event
 
 • For efficacy: 63-day PCR corrected and uncorrected efficacy; 42-day PCR uncorrected efficacy; parasite clearance half-life assessed by microscopy as primary parameter to determine parasite clearance; proportion of subjects with microscopically detectable P. falciparum parasitaemia at Day 3; fever clearance time (i.e. the time taken for the tympanic temperature to fall below 37.5 °C in patients who were febrile at inclusion); proportion of subjects with gametocytaemia during and after treatment stratified by presence of gametocytes at enrolment. • For PK/PD interactions: Pharmacokinetic profiles and interactions (including C_{max} and AUC) of artemisinin-derivatives and partner drugs in ACT and TACT treated subjects in correlation with pharmacodynamics measures of drug efficacy; day 7 plasma levels of partner drugs in correlation with treatment efficacy and treatment arm
Exploratory endpoints	
 • Comparison of 63-day vs 42-day PCR corrected and uncorrected efficacy of ACTs vs TACTs • Proportions of recurrent infections with parasites carrying mutations of known functional significance • Proportions of specimens collected at baseline with parasites carrying mutations of known functional or operational significance (pfkelch13, pfcr, pfmdr1, pfdhfr, pfdhps, pfplasmepsin2, partial or complete deletions of pfhrp2 and other current parasite genetic markers associated with resistance or identified over the course of the study) • Candidate markers of resistance identified through genome wide association studies with in vivo or in vitro parasite drug sensitivity phenotypes • In vitro sensitivity of P. falciparum to artemisinins and partner drugs according to study sites and genotype • Accuracy of SNPs assessment from dry blood spots versus from whole genome sequencing in leukocyte depleted blood samples • Correlation between qPCR based versus microscopy based assessments of parasite clearance dynamics

	
 • Correlation of parasite clearance metrics as assessed by microscopy versus digital microscopy • Comparison of transcriptomic patterns of drug sensitive and resistant parasites before treatment and 6, 12 and 24 hours after start of treatment • Levels of RNA transcription coding for male or female specific gametocytes at admission up to day 14, stratified by the presence of gametocytes at enrolment • Correlation between the host genotype (e.g., CYP2D6, CYP3A4, KCNQ1/LQT1, KCNH2/LQT2, SCN5A/LQT3) and the pharmacokinetics and pharmacodynamics of antimalarials. • Correlations between the place of residence, work, recent travel history assessed by interview and mobile phone records to identify behaviours and risk factors associated with malaria infection. • Correlation between specific antibody titres and measures of drug efficacy

Drugs
 
See Appendix 2 for dosing regimens
	
In Rwanda only:
 
Artemether-lumefantrine+placebo for 3 days.
 
VERSUS
 
Artemether-lumefantrine+amodiaquine for 3 days.
 
All other sites:
 
Artemether-lumefantrine+placebo for 3 days.
 
VERSUS
 
Artemether-lumefantrine+amodiaquine for 3 days.
 
VERSUS
 
Artesunate-mefloquine+placebo for 3 days
 
VERSUS
 
Artesunate-mefloquine+piperavaquine for 3 days
 
Primaquine
 
According to the WHO guideline, all subjects except children under 10 kilograms will also be treated with a single dose of primaquine according to the local requirements or guidelines and WHO treatments schedule as a gametocytocidal treatment. Primaquine will not be deployed in study sites with median to high levels of malaria

	transmission (estimated Annual Parasite Incidence (API) \geq 50 per 1000 population per year according to the WHO World Malaria Report 2017)
--	--

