4.2. Secondary objectives

- To compare the safety and tolerability of ACTs and TACTs within and across sites and regions, including comparisons of 'non-matching' ACTs vs TACTs (AL+PBO versus ASMQ+PPQ, ASMQ+PBO versus AL+AQ).
- To compare additional measures of treatment efficacy between treatment arms, including the 63-day ACPR, the post-treatment prophylactic effect of ACTs and TACTs defined as the 42-day and 63-day PCR uncorrected ACPR, gametocyte carriage, parasite clearance rates and fever clearance.
- To assess pharmacokinetic and pharmacodynamic interactions between antimalarials in TACTs

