#### 2.1.2. Primary endpoint

42-day efficacy defined as PCR-corrected adequate clinical and parasitological response (ACPR).

*(NB, WHO definition of ACPR: absence of parasitaemia at day 42 irrespective of axillary temperature and without previously meeting any of the WHO criteria for early or late treatment failure, or late parasitological failure.)*

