#### 2.1.3. Secondary objectives and endpoints

- To compare the safety and tolerability of ACTs and TACTs within and across sites and regions, including comparisons of 'non-matching' ACTs vs TACTs (AL+Placebo versus ASMQ+PPQ, ASMQ+Placebo versus AL+AQ).
  - Incidence of adverse events and serious adverse events within the first 42 days including markers of hepatic, renal or bone marrow toxicity; cardiotoxicity, in particular QT or QTc-interval above 500 ms at timepoint H4 and H52/H64 and between these time points; change from baseline in haemoglobin at days 3, 7, 28, stratified for G6PD status/genotype; proportion of subjects requiring retreatment due to vomiting within 1 hour after administration of the study drugs; proportion of subjects that reports completing a full course of observed TACT or ACT without withdrawal of consent or exclusion from study because of drug related serious adverse event
  - Changes in the electrocardiogram (such as prolongation of the QTc-interval) in patients treated with TACT versus standard ACT
- To compare additional measures of treatment efficacy between treatment arms, including the 63-day ACPR, the post-treatment prophylactic effect of ACTs and TACTs defined as the 42-day & 63-day PCR uncorrected ACPR, gametocyte carriage, parasite clearance rates and fever clearance.

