***Handling of missing data***

In the ITT analysis in which efficacy will be reported as proportions of outcomes using Complete case Analysis.

In the PP analysis in which efficacy will be reported as proportions of outcomes, patients in which study drugs are discontinued and/or endpoints are not available due to other reasons (such as withdrawal from the study, loss to follow up, *P falciparum* (Pf) or *P vivax* (Pv) reinfections and inconclusive PCR correction) will be excluded from the analysis.

[figure not shown]
In the Kaplan-Meier/survival analysis subjects in which study drugs are discontinued and/or endpoints are not available due to other reasons (such as withdrawal from the study, loss to follow up, Pf or Pv reinfections and inconclusive PCR correction) will be censored or treated as competing risks, as appropriate, from the moment of occurrence of one of these events.

Similar analyses as secondary endpoints will be performed for day 63 PCR corrected efficacy and day 42 and day 63 the PCR uncorrected data as well. Where applicable, we will also report the cumulative reinfection rate. The treatment efficacy, 95% confidence intervals and p-values for the comparison of ACTs with matching TACTs will be presented as outlined in tables 2, 3, 4 and 5 below.

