## STATISTICAL ANALYSIS PLAN

[figure not shown]
**Figure 7 The difference between TACT vs ACT of Day 42 PCR uncorrected Efficacy as proportions by site****Table 4b Comparison of Day 42 PCR uncorrected Efficacy using survival methods of Various ACTs with matching TACTs by sites**

Site	PCR uncorrected ACPR at day 42, Cumulative recurrent infection free percentage (efficacy), % (95% CI)				Hazard ratio (95% CI, p-value)	
	AL+Placebo (N=XXXX)	AL+AQ (N=XXXX)	ASMQ+Placebo (N=XXXX)	ASMQ + PPQ (N=XXXX)	AL+Placebo vs AL+AQ	ASMQ+Placebo vs ASMQ+PPQ
Burkina Faso	XX.X (XX.X - XX.X)	XX.X (XX.X - XX.X)	XX.X (XX.X - XX.X)	XX.X (XX.X - XX.X)	XX.X (XX.X - XX.X, 0.XXX)	XX.X (XX.X - XX.X, 0.XXX)
DR Congo	XX.X (XX.X - XX.X)	XX.X (XX.X - XX.X)	XX.X (XX.X - XX.X)	XX.X (XX.X - XX.X)	XX.X (XX.X - XX.X, 0.XXX)	XX.X (XX.X - XX.X, 0.XXX)
Gambia	XX.X (XX.X - XX.X)	XX.X (XX.X - XX.X)	XX.X (XX.X - XX.X)	XX.X (XX.X - XX.X)	XX.X (XX.X - XX.X, 0.XXX)	XX.X (XX.X - XX.X, 0.XXX)
Guinea	XX.X (XX.X - XX.X)	XX.X (XX.X - XX.X)	XX.X (XX.X - XX.X)	XX.X (XX.X - XX.X)	XX.X (XX.X - XX.X, 0.XXX)	XX.X (XX.X - XX.X, 0.XXX)
Niger	XX.X (XX.X - XX.X)	XX.X (XX.X - XX.X)	XX.X (XX.X - XX.X)	XX.X (XX.X - XX.X)	XX.X (XX.X - XX.X, 0.XXX)	XX.X (XX.X - XX.X, 0.XXX)
Nigeria	XX.X (XX.X - XX.X)	XX.X (XX.X - XX.X)	XX.X (XX.X - XX.X)	XX.X (XX.X - XX.X)	XX.X (XX.X - XX.X, 0.XXX)	XX.X (XX.X - XX.X, 0.XXX)
Tanzania	XX.X (XX.X - XX.X)	XX.X (XX.X - XX.X)	XX.X (XX.X - XX.X)	XX.X (XX.X - XX.X)	XX.X (XX.X - XX.X, 0.XXX)	XX.X (XX.X - XX.X, 0.XXX)
Rwanda	XX.X (XX.X - XX.X)	XX.X (XX.X - XX.X)	XX.X (XX.X - XX.X)	XX.X (XX.X - XX.X)	XX.X (XX.X - XX.X, 0.XXX)	XX.X (XX.X - XX.X, 0.XXX)
All sites	XX.X (XX.X - XX.X)	XX.X (XX.X - XX.X)	XX.X (XX.X - XX.X)	XX.X (XX.X - XX.X)	XX.X (XX.X - XX.X, 0.XXX)	XX.X (XX.X - XX.X, 0.XXX)

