## STATISTICAL ANALYSIS PLAN

**3.10 The selective effect of ACTs versus TACTs on parasites carrying mutations associated with resistance to antimalarial drugs**

Recurrent infections with parasites carrying mutations of known functional significance and specimens collected at baseline with parasites carrying mutations of known functional or operational significance (pfkelch13, pfcrt, pfmdr1, pfdhfr, pfhdps, pfplasmepsin2, partial or complete deletions of pfhrp2 and other current parasite genetic markers associated with resistance or identified over the course of the study) will be summarized as proportions of the total number of samples per site (% and 95% confidence interval) as in table 11.

**Table 12 Recurrent infections and specimens collected at baseline with parasites carrying mutations of known functional significance**

	AL+Placebo (N=XXXX)	AL+AQ (N=XXXX)	ASMQ+Placebo (N=XXXX)	ASMQ + PPQ (N=XXXX)	p-value (AL+Placebo vs AL+AQ)	p-value (ASMQ+Placebo vs ASMQ+PPQ)
Reinfections, n (% CI 95%)	XX.X (XX.X- XX.X)	XX.X (XX.X-XX.X)	XX.X (XX.X- XX.X)	XX.X (XX.X- XX.X)	0.XXX	0.XXX
Pf kelch13, n (% CI 95%)	XX.X (XX.X- XX.X)	XX.X (XX.X-XX.X)	XX.X (XX.X- XX.X)	XX.X (XX.X- XX.X)	0.XXX	0.XXX
Pf crt, n (% CI 95%)	XX (XX.X, XX.X-XX.X)	XX (XX.X, XX.X- XX.X)	XX (XX.X, XX.X- XX.X)	XX (XX.X, XX.X- XX.X)	0.XXX	0.XXX
Pf mdr1, n (% CI 95%)	XX.X (XX.X- XX.X)	XX.X (XX.X-XX.X)	XX.X (XX.X- XX.X)	XX.X (XX.X- XX.X)	0.XXX	0.XXX
Pf dhfr, n (% CI 95%)	XX.X (XX.X- XX.X)	XX.X (XX.X-XX.X)	XX.X (XX.X- XX.X)	XX.X (XX.X- XX.X)	0.XXX	0.XXX
Pf dhps, n (% CI 95%)	XX.X (XX.X- XX.X)	XX.X (XX.X-XX.X)	XX.X (XX.X- XX.X)	XX.X (XX.X- XX.X)	0.XXX	0.XXX
Pf Plasmepsin 2, n (% CI 95%)	XX.X (XX.X- XX.X)	XX.X (XX.X-XX.X)	XX.X (XX.X- XX.X)	XX.X (XX.X- XX.X)	0.XXX	0.XXX
Partial or complete deletions of PF hrp2, n (%, CI 95%)	XX.X (XX.X- XX.X)	XX.X (XX.X-XX.X)	XX.X (XX.X- XX.X)	XX.X (XX.X- XX.X)	0.XXX	0.XXX
Others, n (% CI 95%)	XX.X (XX.X- XX.X)	XX.X (XX.X-XX.X)	XX.X (XX.X- XX.X)	XX.X (XX.X- XX.X)	0.XXX	0.XXX

---

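### The post-treatment prophylactic effect is defined as PCR-uncorrected ACPR, which mixes cure with prevention of new infection; the distortion is small at the planning values, but the measure does not answer the question it is named for

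*Protocol*

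**What the plan says.** The definition appears three times in almost the same words. The protocol synopsis refers to the "post-treatment prophylactic effect of ACTs and TACTs defined as the 42-day & 63-day PCR uncorrected ACPR". Protocol section 4.2 and SAP section 2.1.3 repeat it, the latter as "the post-treatment prophylactic effect of ACTs and TACTs defined as the 42-day & 63-day PCR uncorrected ACPR".

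SAP section 2.1.2 says what ACPR requires: no parasitaemia at day 42, "without previously meeting any of the WHO criteria for early or late treatment failure, or late parasitological failure". The survival version in SAP Table 4b is headed "PCR uncorrected ACPR at day 42, Cumulative recurrent infection free percentage (efficacy), % (95% CI", and Table 5b does the same for day 63. Both therefore count any recurrence.

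The SAP also refers to new infections in three other places:

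- Section 3.3: "Where applicable, we will also report the cumulative reinfection rate". No table shell or between-arm contrast goes with it.
- Section 3.3, survival analysis: "Pf or Pv reinfections and inconclusive PCR correction) will be censored or treated as competing risks, as appropriate". This treats new infections as something to remove from the corrected estimate.
- Table 12, under the objective on resistance mutations: a row labelled "Reinfections, n (% CI 95", by arm, with a p-value for each matching pair.

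**The concern.** Post-treatment prophylaxis is protection against new infection while drug remains in the blood. Recrudescence is failure to clear the treated infection. The trial pays for PCR correction to tell the two apart and rests its primary endpoint on that distinction, yet the measure assigned to prophylaxis puts them back together.

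Two errors follow. If the TACT cures more patients but protects no longer, the plan's measure still favours it. The cure effect is then reported once as corrected efficacy (Tables 2 and 3) and again within the measure assigned to prophylaxis (Tables 4 and 5). If the TACT cures more but protects for a shorter time, the two effects can cancel and the measure shows no difference. The sample-size section says TACT may be 1 to 2 points better on corrected efficacy, so the direction of the first error is the one the trial itself expects.

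**Working it through.** **Inputs from the documents** (Protocol 15.1, SAP 2.2.1): ACT corrected efficacy 96%; TACT 97% to 98%; 60 ACT and 120 TACT evaluable per pair per site; margin 6 points; one-sided alpha 0.025; about 80% power. The AL pair runs at 8 sites, giving 480 and 960 evaluable when pooled.

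**Assumed:** a reinfection risk *r* that is the same in both arms and independent of recrudescence. The documents give no rate, so *r* runs from 10% to 50%.

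**The plan's own figure.** The documents give no figure for the prophylactic effect, so I checked the planning values instead. Non-inferiority power = Φ[(0.06 + pT − pC)/SE − 1.96], with SE = √(0.96×0.04/60 + pT(1−pT)/120). At pT = 98% this is 80.6%, which reproduces the stated 80%. At pT = 97% it is 65%. I carry both values forward.

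**Size of the artefact.** Uncorrected ACPR = corrected efficacy × (1 − *r*). With equal *r* the true prophylactic difference is zero, so any difference is artefact. The chance of p<0.05 comes from a two-sided unpooled z-test.

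| ACT vs TACT cure | *r* | Uncorrected ACPR | Artefact (points) | p<0.05, pooled 480/960 | p<0.05, one site 60/120 |
|---|---|---|---|---|---|
| 96% vs 97% | 10% | 86.4% vs 87.3% | 0.9 | 7.6% | about 5% |
| | 30% | 67.2% vs 67.9% | 0.7 | 5.8% | about 5% |
| | 50% | 48.0% vs 48.5% | 0.5 | 5.4% | about 5% |
| 96% vs 98% | 10% | 86.4% vs 88.2% | 1.8 | 16% | about 6% |
| | 30% | 67.2% vs 68.6% | 1.4 | 8% | about 5% |
| | 50% | 48.0% vs 49.0% | 1.0 | 6% | about 5% |

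On the hazard-ratio scale of Table 4b, ln(TACT)/ln(ACT) for 96% vs 98% is 0.86, 0.95 and 0.97 at these three rates. The true value for new infection is 1.

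**If ACT cure is much lower than planned** (illustrative 90% vs 98%, *r* = 20%): 0.90×0.80 = 72.0% and 0.98×0.80 = 78.4%, an artefact of 6.4 points. SE = √(0.72×0.28/480 + 0.784×0.216/960) = 0.0244; 0.064/0.0244 = 2.62; Φ(2.62 − 1.96) ≈ 75% pooled.

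**Masking.** Keep 90% vs 98% cured, but let reinfection be 20% under ACT and 26.5% under TACT. Then 0.90×0.80 = 72.0% and 0.98×0.735 = 72.0%. The 6.5-point loss of protection disappears.

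**Check on the replacement measure.** Cumulative incidence of new infection, with recrudescence as a competing event, is also shifted by cure, because the better-curing arm leaves more patients at risk. With constant hazards a = −ln(cure) and b = −ln(1 − *r*), it equals [b/(a+b)] × [1 − cure×(1 − *r*)]. At 85% vs 97% with equal reinfection hazards this gives 27.8% vs 29.6% (*r* = 30%) and 46.6% vs 49.3% (*r* = 50%), both against the TACT. The cause-specific hazard ratio is 1 by construction in the same scenarios. The between-arm contrast should therefore use the hazard ratio.

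**The case against.** **The effect is small where the trial expects to be.** This stands. At the planning values the artefact is under 2 points, and at a single site the false-positive chance hardly moves from 5%.

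**The results tables do not use the word prophylaxis.** Tables 4 and 5 are titled as uncorrected efficacy, and the endpoint lists use that term too. This is true and limits the harm, but the objective in three places still says that those results define the prophylactic effect.

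**The information is already in the outputs.** This stands in part. Corrected and uncorrected results will both be tabulated by site, so a reader can see whether cure drives a contrast. Subtracting one from the other does not recover the effect, though. Corrected analyses exclude reinfections (per protocol) or censor them or treat them as competing risks (survival), so denominators and risk sets differ and no interval results. It would also be wrong to say that the SAP never compares reinfection between arms, because Table 12 has p-values for it. That row belongs to another objective, states no time point and gives no effect estimate. The cumulative reinfection rate in 3.3 is conditional and likewise has no stated time point or contrast.

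**Two stronger readings a reader might infer.** One is that a false prophylactic finding is nearly certain. With 85% vs 97% cure, the pooled chance of p<0.05 is about 100%, 88% and 58% at 10%, 30% and 50% reinfection. Those cure rates are not in the documents, and the figures need ACT efficacy of 85% at all eight sites. The other is that Rwanda already shows rising ACT failure. Protocol section 3.2 reports falling incidence and early signs of artemisinin resistance, and speaks of ACT failure only as something that may come.

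**Conclusion.** The point holds as a mismatch between a secondary objective and its measure. Uncorrected ACPR combines cure with prophylaxis, and no output named as the prophylaxis measure separates them. The direction of the bias follows the cure difference whatever the reinfection rate; its size does not.

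At the planning values the artefact is about 0.5 to 1.8 points, with a 5% to 16% pooled chance of p<0.05. It reaches 6.4 points and about 75% in an illustrative case where ACT cure falls to 90%. These figures assume equal reinfection in both arms, independence from recrudescence, and 480 and 960 evaluable patients in the AL pair. The primary endpoint is not affected. The change is worth making because it is cheap and because masking cannot be seen from the defined measure alone, but the documents do not support calling it a serious threat to the trial's conclusions.

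**What to change.** In protocol sections 2 and 4.2 and SAP sections 2.1.3 and 3.3:

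- Define the post-treatment prophylactic effect as time to first PCR-confirmed new *P. falciparum* infection, by day 42 and by day 63.
- Compare matching arms by cause-specific hazard ratio with a 95% CI, censoring at recrudescence. Stratify by site in the all-sites row.
- Show cumulative incidence by arm, with recrudescence as a competing event, as a description only.
- Keep Tables 4 and 5, labelled *any recurrence (cure plus prophylaxis)*.

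No new data, visits or patients are needed; the work is a wording change and one further table. There are two costs. The new measure depends on PCR classification, which uncorrected ACPR does not, although the primary endpoint already carries that dependence. And because the definition sits in the protocol objectives, a protocol amendment is needed as well as a SAP edit; under protocol section 19.3, an amendment judged substantial goes to the ethics committees.
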